### **E.3. Aim 3: Conduct a Comprehensive Cost Study**

Building upon previous research, which reported that a glaucoma follow-up unit was cost effective compared to usual care, we will conduct a comprehensive cost study to estimate the intervention costs and cost-effectiveness of detecting eye diseases and vision impairment in a high-risk population. We have proposed an economic framework to minimize program costs, maximize program impact, and measure return on investment.

Building upon research by Holtzer-Goor KM, which reported that a glaucoma follow-up unit was cost effective compared to usual care, we will analyze the cost effectiveness of our enhanced intervention. The cost analysis will assess the feasibility of the study and identify areas where program costs can be minimized to estimate the net cost of replicating the intervention in additional communities to achieve similar outcomes once development and evaluation costs are removed.

E.3.a. Cost Measures for Aim 3: Cost measures will include intervention costs, glaucoma-related healthcare service use, glaucoma-related medications, and patient travel costs. The glaucoma exams of this project consist of five steps conducted by ophthalmic technicians, ophthalmologists, and study staff. The main tests performed on the patient include fundus photography, visual acuity, and a visual field analysis. Intervention costs will be measured for each step in the examination process and will include human costs as well as non-human costs. Trained research assistants and fellows will conduct site visits to observe and record the time each staff member takes to complete each step.

Direct personnel costs are calculated based on the mean duration for each step. Wage rates for personnel will be obtained based on job classifications, available from the 2013 US Bureau of Labor Statistics for Philadelphia. It

is assumed that most of the steps could be performed by ophthalmic technicians or medical assistants, whose wage rate is approximately \$16 per hour. Physicians participating in this project are estimated to have a wage rate of approximately \$87 per hour. Fringe benefits will be added to the wage costs at an estimated 35%. Time costs for each step are calculated with the following equation:

$$\text{Staff member} = \text{mean \# of minutes} \times (\text{wage rate} + \text{benefits})$$

If additional staff members assisted with a step, then it will be assumed that they were there for half the time and additional time costs will be calculated as:

$$\text{Additional staff members} = (\text{mean \# of minutes}/2) \times (\text{wage rate for medical assistant} + \text{benefits})$$

Non-human costs to be collected include telemedicine platform, medical equipment and supplies, office supplies, community partners' recruitment, communication (internet hotspots), van rental and maintenance, and travel inclusive of fuel, and mileage. Medical equipment is expensive; however, it has been shown that once the investment is made, the operational costs are fairly low. Since the telemedicine platform and the medical equipment have been donated from WETD and the previous CDC-funded project, the cost of this study will be dramatically reduced.

The intervention will be examined to determine which services are billable to healthcare insurers, and the extent to which such reimbursement covers the costs. Even though it may not have a direct impact on exams, data on patient travel will also be collected. During check-out, project staff will ask patients about their satisfaction and type of transportation used. The costs of the transportation methods will be estimated based on the reported fares from Southeastern Pennsylvania Transportation Authority (SEPTA). Buses and subways cost \$2.25 per ride. Customized Community Transportation (CCT), for elderly and handicapped individuals, costs \$4 each way. When patients drive or take taxis, costs are estimated at \$1.65 and \$15 each way, respectively. Individuals who walk have no transportation costs. Previous studies have shown that "convenience of travel" contributed to patient satisfaction. Previous research has also reported that decreased patient traveling saved \$55 per visit. Additionally, work-productivity costs may be considered, since we are recruiting people who may be employed.

E.3.b. Effectiveness Measure for Aim 3: In addition to conducting a comprehensive examination of costs, we will systematically examine these costs in the context of the intervention's societal benefits by conducting a formal cost-effectiveness analysis. The cost-effectiveness analysis will employ quality-adjusted life years (QALYs) as the primary measure of societal benefits. We will capture QALY over the course of 2 years using the Health Utilities Index, v.2/3 (HUI-2/3). HUI-2/3 is a utility measurement instrument that consists of 15 items that capture 8 attributes of health-related QoL: vision, hearing, speech, ambulation, dexterity, emotion, cognition, and pain.

The scoring algorithm will be obtained from Health Utilities, Inc. and is based on Canadian health preference weights. Utility scores from this instrument range from 0-1, with a higher score indicating better quality-adjusted life. Previous research has shown that the HUI-3 has consistent validity in people with glaucoma, diabetic retinopathy, and cataracts. QALY will be measured as the amount of utility gained or lost over each year of the program.

E.3.c. Incremental Cost-Effectiveness Ratio: The primary cost-effectiveness measure will be defined as the incremental difference between cost of the enhanced intervention and usual care, divided by the difference in health utility-Incremental Cost Effective Ratio (ICER). The ICER thus will indicate the additional costs to bring about one additional unit of benefit (QALY) from the enhanced intervention compared to usual care. The

reference case, which will be defined as usual care. The ICER obtained will be compared to acceptable thresholds of \$50,000 to \$100,000-QALY. A secondary measure will be cost per diagnosis made.

E.3.d. Sensitivity Analysis for Aim 3: To account for uncertainty in our primary ICER, cost and effectiveness data will be entered into a decision analytic model. This is particularly important since the study will be powered based on the primary outcome, not the cost-effectiveness measure. Sensitivity analyses will ensure robustness of the ICER. Both univariate sensitivity analysis (whereby 1 variable is changed at a time and impact on the ICER will be examined), and probabilistic sensitivity analysis (PSA), whereby all relevant variables are simultaneously modified within reasonable ranges will be conducted. Sensitivity analyses will include those variables where we anticipate “real world” uncertainty.

The PSA will consist of a Monte Carlo simulation model based on estimated distributions for each variable in the model, with each distribution based on the mean and standard deviation of all probabilities, costs, and effectiveness measures. If the standard deviation of a variable is not available, it will be assumed to be 10% of the mean. The simulation will consist of 10,000 random iterations, with the goal of determining the likelihood that the enhanced intervention is cost-effective compared to usual care. The PSA will be performed using the TreeAge Pro software program (Williamstown, MA). Since the trial employs a time horizon of >1 year, discounting future costs and benefits will be performed at a rate of 3% each year beyond the first.

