**C.6.a. National Eye Institute-Visual Function Questionnaire (NEI-VFQ):** A member of the research team will consent all patients and administer the validated NEI-VFQ-25 questionnaire at Visit 2, Visit 5 and Visit 8 to assess barriers and the influence of their vision impairment on their health-related quality-of-life. The 12 subscales are calculated by adding the relevant items and transforming the scores into a scale from 0 to 100. Higher scores indicate better quality-of-life. The composite score will be calculated as the average of 12 subscale scores. Patient navigators will use these results to assess barriers and refer patients to appropriate professionals, such as a social worker, low vision specialist, psychiatrist, occupational therapist, Medicare/Medicaid insurance advisor, and/or cataract surgeon. All materials will be culturally and linguistically appropriate and translated into other languages as necessary using trained medical interpreters and we will track all process measures.

\*NEIVFQ surveys will be administered in person to all patients at Visit 2. For Visits 5 and 8 questionnaires will be administered over the phone by a patient navigator or social worker.

**C.6.b. Patient Satisfaction Survey:** With assistance from Westat, our partners, and Advisory Board members, we will create a new survey instrument and administer it at the end of each of the study visits. We will ask patients to rate their satisfaction with the exam, its duration, its convenience, the staff, and the likelihood of attending a follow-up eye exam. These surveys will optimize patient engagement and report outcomes that are important to patients and stakeholders.

\*Satisfaction surveys will be administered in person to all patients for Visits 1 and 2. For Visit 5 surveys will be administered over the phone by a patient navigator or social worker for all enrolled patients. For Visits 3, 4, 6, and 7 satisfaction surveys will be administered according to randomization. For Visit 8 (or final visit), a Study Closeout Satisfaction Survey will be administered at the primary care office by a member of the study team.

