**D.1.b. Effectiveness/Efficacy:** We will evaluate the impact of our enhanced intervention on our proposed outcomes, including quality-of-life, and economic efficiency. Determining the effectiveness of our intervention is critically important because patients with undetected glaucoma and other eye diseases can suffer lasting visual impairment that can affect their quality-of-life, economic status, morbidity, and ultimately mortality. New strategies are necessary to improve patient access and utilization of eye care. Our study aims to determine if adherence to follow-up recommendations changes as a result of the enhanced intervention. We will determine the effectiveness of the intervention by examining the effect size associated with our intervention and specified outcomes (adherence to follow-up recommendations and vision-related quality-of-life).

**D.1.c. Adoption:** Our letters of support from Advisory Board members and partner institutions demonstrate a strong commitment and willingness to participate in this research study. We are working closely with primary care offices, health centers, universities, governmental agencies, and community organizations. We expect to notice variations in patient behavior based on the number of resources available to them. These varying settings and intervention modalities are critical to the current and potential impact of our intervention. If differences exist among sites, this is evidence of differential adoption.

**D.1.d. Implementation:** At each setting, implementation refers to the intervention agents' fidelity to all elements of the protocol. This includes consistency of delivery as intended and the time and cost of the intervention. Investigators in coordination with Westat and the project manager will determine the extent to which the intervention was delivered. We will assess implementation by reporting on the percentage of process objectives that were achieved, such as: What proportion of patients received the confirming diagnosis enrolled in the study? How many patients followed up with the general ophthalmologists at the initial 6-month, 1-year, 2-year, and 3-year visits. We will also conduct a cost analysis and report costs of all levels of the intervention, including recruiting patients, reading images, confirming diagnoses, randomization, and 3-year follow-up (Table 7).

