## **E.2. Data Analysis for Aims 1 and 2**

**E.2.a. Primary Analysis for Aim 1:** The primary analysis for Aim 1 will be to estimate the positive predictive value (PPV) of the teleophthalmology intervention for diagnosing of glaucoma. We hypothesize that the diagnosis of glaucoma and glaucoma suspect using undilated optic disc images, tonometry pressure results, and medical history will predict the comprehensive eye exam diagnosis. That is, we will calculate the proportion of patients diagnosed with glaucoma or glaucoma suspect whose diagnosis was confirmed at Visit 2 with an exact two-sided binomial confidence interval. We will conclude that the telemedicine intervention has good performance if the lower bound of the confidence interval is above 80%.

The expected sample size for this aim is 250 patients as we anticipate approximately 50% of those diagnosed with eye pathology and who return for the confirmation Visit 2 will have been diagnosed with glaucoma or glaucoma suspect at Visit 1. Data from Maa (2014) can be used to estimate the PPV for glaucoma at 85%. With 250 patients, we have 50% power to conclude the PPV is greater than 80% if the true PPV is 85% and over 99% power to conclude the PPV is greater than 80% if the true PPV is 90% using a 2-sided test with alpha=0.05. We will repeat this analysis looking at the proportion of patients diagnosed with eye pathology who in fact have an ocular diagnosis (whether or not the exact abnormality was correct).

**E.2.b. Primary Outcome Measure for Aim 2:** Patient baseline demographic and clinical characteristics will be summarized overall and by randomization assignment (in Aim 2) using means, medians, standard deviations, and ranges or frequencies and percentages, as appropriate. Our general approach from the randomized trial is to analyze patients as randomized regardless of the amount of intervention received. The primary outcome measure for Aim 2 is attendance at recommended follow-up visits (Visit 4 and later). Since the expected

number of appointments will differ based on diagnosis and disease severity, which may change over time, attendance will be summarized annually.

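### The ICER limits care costs to glaucoma, while its QALYs come from a trial that also randomises patients with other eye disease

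*Combined protocol and SAP*

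**What the plan says.** E.3.a lists the cost inputs: "Cost measures will include intervention costs, glaucoma-related healthcare service use, glaucoma-related medications, and patient travel costs". It then describes how the first item is obtained: "Intervention costs will be measured for each step in the examination process and will include human costs as well as non-human costs". Further resources follow: "Non-human costs to be collected include telemedicine platform, medical equipment and supplies, office supplies, community partners' recruitment, communication (internet hotspots), van rental and maintenance", together with travel. On lost work it says only that "work-productivity costs may be considered, since we are recruiting people who may be employed".

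On the effect side, E.3.b says: "The cost-effectiveness analysis will employ quality-adjusted life years (QALYs) as the primary measure of societal benefits". The instrument is the HUI-2/3, which scores eight health attributes, vision among them, over 2 years. E.3.c divides the between-arm cost difference by the utility difference and compares the result with $50,000 to $100,000 per QALY.

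Aim 2 and C.9 do not confine randomisation to glaucoma. Patients with other eye conditions or impaired vision are included, and E.2.b analyses patients as randomised. C.6.a has navigators refer patients to a "low vision specialist, psychiatrist, occupational therapist, Medicare/Medicaid insurance advisor, and/or cataract surgeon", among others. D.1.d promises to "report costs of all levels of the intervention, including recruiting patients, reading images, confirming diagnoses, randomization, and 3-year follow-up".

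**The concern.** A cost-effectiveness ratio is interpretable only if the numerator counts the resources that produce the gain in the denominator. Here the health-service and drug costs are tied to one disease. The patients and the utility instrument are not.

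A patient with cataract or retinopathy who attends because of a navigator may gain vision, and so utility. On the wording of E.3.a, the visits, procedure and medication behind that gain are not counted.

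At stake is Hypothesis 3, that the enhanced intervention is cost-effective by commonly cited thresholds. A numerator that leaves out part of the induced care would tend to favour that conclusion.

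**Working it through.** The documents state no ICER, incremental cost or QALY difference, so there is no planned figure to reproduce. The check compares scopes and then gives an illustration.

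**Scope of cost and effect**
- Care and drug costs: glaucoma-related (E.3.a). E.3 lists no other eye care.
- Patients: consented, eligible patients who complete Visit 2, whatever the eye diagnosis (Aim 2, C.9).
- Utility: generic. E.3.b supports the HUI-3 by its validity in retinopathy and cataract as well as glaucoma.
- Aim 3 itself concerns eye disease and vision impairment in general.
- E.3 names no analysis population. That all randomised patients contribute QALYs is inferred from the general rule in E.2.b.

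**How many patients are affected**
- E.2.a plans on glaucoma or suspect in "approximately 50% of those diagnosed with eye pathology" who return for Visit 2, by their Visit 1 diagnosis. That leaves about 50% with something else.
- In the preliminary glaucoma project (C.2.b, Table 3), glaucoma-type diagnoses number 52 + 276 + 155 = 483 and other disease needing follow-up 92 + 52 = 144. The share is 144/(483 + 144) = 144/627 = 23%.
- That project recruited by age and race. This trial also recruits on diabetes, and in the diabetes teleophthalmology project (C.3.c) 24% showed retinopathy against about 6% glaucoma suspect. The 23% may therefore be low for this trial.
- Neither figure describes the randomised set, whose mix is not stated.

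**The intervention-cost item**
- E.3.a itemises staff time by examination step. Visits 1 and 2 are given to both arms and normally precede randomisation, so their costs largely cancel in the difference.
- What differs by design is navigator and social-worker work (C.7, C.8, C.8.a). E.3 does not itemise it.

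**Sensitivity analysis**
- E.3.d varies inputs that are in the model. It cannot vary a cost category that was never collected.

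**Illustration**

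From the plan: a 20-point adherence gain (Table 10), 2 years (E.3.b), and the two shares above. Assumed, not in the documents: 1 to 2 visits per year, $100 to $200 per visit, and a QALY gain of 0.005 to 0.02.

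Omitted cost per randomised patient = share × 0.20 × visits per year × 2 × cost per visit. ICER shift = omitted cost / QALY gain.
- Share 50%: 0.50 × 0.20 × 1 × 2 × $100 = $20, up to 0.50 × 0.20 × 2 × 2 × $200 = $80. Shift: $20/0.02 = $1,000 to $80/0.005 = $16,000 per QALY.
- Share 23%: $9.20 to $36.80 by the same formula. Shift: $9.20/0.02 = $460 to $36.80/0.005 = $7,360 per QALY.

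This prices extra visits only. Procedures would add to it, and averted later care would subtract.

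Navigator time would matter only if it were actually left out. At the plan's technician or assistant rate, $16 × 1.35 = $21.60 per hour, an assumed 1 to 5 hours per patient is $21.60 to $108. That is $21.60/0.02 = $1,080 to $108/0.005 = $21,600 per QALY.

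**The case against.** The strongest reply is that the plan's costing is wider than its one restrictive adjective. Travel, platform, equipment, supplies, recruitment and van costs are all listed, productivity costs are possible, and D.1.d promises costs at every level of the intervention through 3-year follow-up. This stands: the ICER does not rest on glaucoma-related and examination costs alone.

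A reader might also infer that navigator and social-worker time is excluded. The documents do not support that. Intervention cost is the first listed item, the enhanced intervention is defined by those staff, and E.3.c takes the cost difference between the arms. Their time is not itemised, which is different from being ruled out. Nor are all examination steps common pre-randomisation procedures: Table 5 also schedules acuity and visual field at Visits 3 to 8.

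A third reply concerns direction and size. Earlier treatment of non-glaucoma disease might avert later costs, and at the low end of the illustration $460 per QALY is under 1% of the $50,000 threshold. This also stands.

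Finally, Aim 3 is not the basis of the trial's power, and the funder reviews the cost strategy. That limits the weight of the point. It does not remove the mismatch, because none of these replies brings non-glaucoma eye services and medications into the numerator.

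**Conclusion.** The point holds as a mismatch of scope. E.3.a restricts service and medication costs to glaucoma, while the randomised population and the HUI-2/3 cover other eye disease. The likely effect is an understated ICER, because an intervention that raises attendance should also raise non-glaucoma care costs. This is probable, not certain.

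The size cannot be computed from the documents. The $460 to $16,000 per QALY rests on assumed visit numbers, visit costs and QALY gains, and on a non-glaucoma share between 23% and 50%. At the upper end it could change the conclusion against a $50,000 to $100,000 threshold. At the lower end it would hardly do so.

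A reader might infer that half of the randomised patients have other eye disease. The 50% is a planning value for Visit 2 attenders and does not establish that. The navigator and social-worker item is a missing specification that deserves attention, because time not logged as it is spent is hard to recover.

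**What to change.** In E.3.a, replace the glaucoma-related qualifier with eye-related services, procedures and medications, counted for every randomised patient. State in E.3 that the primary ICER uses all randomised patients for both costs and QALYs. An ICER limited to glaucoma and glaucoma suspect, with cost and QALY both restricted, can be a secondary analysis.

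Define the incremental intervention cost as navigator and social-worker time, mailings, interpreters and arranged transport, recorded per patient by arm. Value staff time with the existing wage formula and a rate suited to a social worker.

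Much of the material is already gathered. C.7 provides for access to follow-up records, E.1.c tracks visits, and Table 8 counts referrals, prescriptions, laser, surgery, transport and interpreter use. Counts are not costs, however. The change needs a simple time log, unit costs for non-glaucoma eye care, and some added abstraction of services delivered elsewhere, such as low-vision care. The resulting ICER will probably look less favourable.

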#### **C.4. Research Design and Methods**

**C.4.a: Project Overview:** The Wills Eye Glaucoma Research Center will conduct a 5-year prospective, randomized controlled trial to evaluate an innovative, community intervention using posterior fundus photographs of the optic nerve and macula to improve access and utilization of eye care to detect, treat, and manage high-risk patients with previously undiagnosed glaucoma, glaucoma suspect, and other eye diseases. L. [name]; [name]; and [name], RD, will lead the research study.

Our diverse targeted, at-risk population includes African Americans, Hispanics, and Asians over age 40; other older adults (aged 65+); individuals over age 40 with a family history of glaucoma and/or with diabetes. Approximately 1250 patients will be recruited from geographically diverse locations across Philadelphia and Chester counties, with the help of our community partners. **Phase 1** will consist of detecting eye disease in 7

primary care offices and 10 FQHC using telemedicine (Visit 1), followed by a comprehensive eye exam by a Wills glaucoma specialist in the same setting to confirm the diagnosis (Visit 2). Based on preliminary data, 30% of patients (approximately 750) will have abnormal optic nerve and/or macula images. The predictive accuracy of the optic nerve images to detect glaucoma and glaucoma suspect as confirmed by the comprehensive eye exam will be evaluated.

**Phase 2** will involve consenting, enrolling, and randomizing 374 patients to either the usual care group (n=187) or the enhanced intervention group (n=187). The enhanced intervention will consist of using patient navigators and a social worker to reduce barriers to follow-up eye care. **Phase 3** will consist of following patients proximally (6 months) and distally (3 years) while they attend appointments with a local, eye care provider (Visits 3-7). Adherence to follow-up recommendations for eye care will be the primary outcome measure. A comprehensive cost study to estimate the intervention costs and cost-effectiveness of detecting eye diseases and vision impairment in a high-risk population will also be conducted. Protocols, materials, outcomes, and results will be disseminated to other communities in order to expand detection of glaucoma, other eye diseases, and visual impairment, and to further refine these approaches to successfully scale the program up to a national level.

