C.8. Patient Navigation Protocol (Appendix I): The use of patient navigators and social workers has proven successful in cancer care programs, showing higher rates of follow-up care, while increasing patient satisfaction and decreasing anxiety. Patient navigation shows promise as the missing link between available services and healthcare delivery to vulnerable populations. By educating and guiding patients, navigators can lessen the disparities among racial/ethnic groups at risk for eye disease. Our study staff, project managers, ocular technicians, and research assistants have been trained to serve as patient navigators. Their responsibilities will include: phoning patients to schedule appointments; confirming appointments by mailings, emails and/or text messaging; arranging transportation through Customized Community Transportation (CCT) and Philadelphia Paratransit Service; and scheduling trained medical interpreters.

Wills Eye ocular technicians will also assist patients in the enhanced intervention group across 17 sites with medication refills and obtaining free medications from pharmaceutical companies. Our patient navigators can identify cultural and language differences and are aware of health literacy issues. We will also provide multiple outreach strategies as additional barriers are identified. Results will be discussed at our weekly research team meetings, quarterly meetings with each partner, and annual meetings with our Advisory Board.

C.8.a. Identifying Barriers to Follow-up Using Social Workers: Research shows that individuals at high risk for glaucoma are not likely to participate in screening programs or ongoing follow-up with an ophthalmologist in an office-based setting. Appendix J describes how innovative approaches to identifying and remediating barriers have been accomplished in our current CDC glaucoma detection program and can be tested, refined, and implemented in this proposed study (Section C.2.a). Educational materials may help non-adherent patients to understand the benefits of taking glaucoma medications regularly.

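### E.3.a costs only examination steps common to both arms, so the E.3.c ICER has no planned data source for navigator and social worker time

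*Combined protocol and SAP*

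**What the plan says.** The contrast between the arms is set out in C.4.a: "The enhanced intervention will consist of using patient navigators and a social worker to reduce barriers to follow-up eye care". C.7, C.8 and C.8.a add the content: scheduling and reminder calls, transport and interpreter arrangements, contact by a part-time medical social worker, and help with "medication refills and obtaining free medications from pharmaceutical companies".

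Aim 3's primary measure, in E.3.c, is the ICER. Its numerator is the "incremental difference between cost of the enhanced intervention and usual care", and its denominator is the difference in health utility.

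E.3.a lists what will be costed: "Cost measures will include intervention costs, glaucoma-related healthcare service use, glaucoma-related medications, and patient travel costs". It then makes the first of these concrete. The object of costing is a five-step eye exam, built mainly on photographs of the fundus, acuity and visual fields, and the rule for it is: "Intervention costs will be measured for each step in the examination process and will include human costs as well as non-human costs". Staff time is observed at site visits and valued at about $16 an hour for technicians or medical assistants and $87 for physicians, plus 35% benefits. The non-human items are telemedicine, equipment, supplies, recruitment, communication, van and travel. Patient travel has its own fares, including $4 each way for the paratransit service.

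D.1.d says that costs will be reported for every level of the intervention, through three years of follow-up.

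**The concern.** The resources that E.3.a tells staff to measure are not the resources that differ between the arms. An ICER needs the cost difference created by the assignment, and here that difference includes people making calls, arranging services and working through barriers. E.3.a to E.3.d name neither navigators nor the social worker, and provide no time record or unit cost for their work.

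Hypothesis 3 says that the enhanced arm will be cost-effective. A numerator without the enhanced arm's own labour is too low, which favours that hypothesis. Minutes spent on telephone contacts are also hard to recover reliably once three years have passed, so the gap needs closing while contacts are still being made.

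**Working it through.** The plan states no incremental cost, navigator cost or ICER, so there is no figure to reproduce. The check has two parts: where the costed steps fall relative to randomisation, and what the uncosted labour might amount to.

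**1. Do the costed steps differ by arm?**
- Table 5 has fundus photographs at Visit 1 only. The study team's own visual field test is at Visit 2 (C.6).
- C.9 randomises patients who have completed Visit 2. The exception in C.5.c, for high eye pressure, randomises at Visit 1 and skips Visit 2, and it applies whichever arm is then assigned.
- Exam-step cost is therefore the same in expectation in both arms. With the per-participant figures of the preliminary project (C.2.c): $42.44 + $87.34 = $129.78 in each arm, and $129.78 − $129.78 = $0 increment.

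**2. Is the labour captured anywhere else?**
- Table 7 tracks time per patient and per eye exam and does not tie it to navigator or social worker contacts. Its contact log is the source for partner engagement.
- Table 8 counts letters and calls for recruitment and Visit 1, ticked for Phase 1 only. Navigator calls for later visits are not counted.
- Table 8 counts use of interpreters, transport and medication assistance. E.3.a has fares for transport but no unit cost for interpreters or for drugs supplied free.
- On travel, E.3.a says: "During check-out, project staff will ask patients about their satisfaction and type of transportation used". Visits 3 to 7 are at local eye care practices, so the plan should say how transport type is obtained for those visits. That is a data-capture point. The fares themselves are specified.

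**3. Illustrative size of the omitted labour**

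From E.3.a: $16 × 1.35 = $21.60 per hour. Hours and QALY gain are assumptions, because the documents give neither. Discounting is ignored.

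Omitted cost = hours × $21.60. Understatement of the ICER = omitted cost ÷ QALY gain.

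| Assumed navigator time per patient | Cost | per QALY, gain 0.05 | gain 0.01 | gain 0.005 |
|---|---|---|---|---|
| 15 min × 5 visits = 1.25 h | $27 | $540 | $2,700 | $5,400 |
| 1 h × 5 visits = 5 h | $108 | $2,160 | $10,800 | $21,600 |
| 3 h × 5 visits = 15 h | $324 | $6,480 | $32,400 | $64,800 |

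The five visits are Visits 3 to 7. Social worker time would be added to each row. E.3.c compares the ICER with $50,000 to $100,000 per QALY.

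**The case against.** A reader might infer that the plan excludes the cost of the tested intervention from its ICER. It does not say so. E.3.c places that cost in the numerator, E.3 states that the cost-effectiveness of the enhanced intervention will be analysed, and D.1.d commits to costs at all levels. The intention is there. What is absent is a measurement rule to carry it out, and the one rule given measures something else.

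A reader might also infer that most of the enhanced arm's extra cost is lost. The documents do not show this. Glaucoma-related service use and medications are listed costs and can differ by arm after randomisation. If navigation raises attendance, they could exceed navigator labour. Nor is transport omitted: E.3.a prices patient travel, including the paratransit fare for a service that navigators arrange, so it does not belong in the figures above.

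Wages are not wholly missing either. E.3.a takes rates by job classification, and C.8 includes ocular technicians among the navigators, so the $16 rate covers some of them. The social worker has no stated rate.

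E.3.d does not list its model inputs, so it cannot be said that navigator cost is barred from the sensitivity analysis. But the simulation draws on the mean and standard deviation of each variable. A cost never collected could enter only as an assumption.

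Exam-step costing also has a proper use: Aim 3 covers the cost of detection, and E.3.c names cost per diagnosis as a secondary measure. Finally, the navigation protocol is in Appendix I, which is not reproduced in the public document and may hold a contact record. E.3 does not refer to one.

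These points narrow the claim and leave its core standing: the stated rule for intervention cost contributes about zero to the increment, and no section supplies navigator or social worker time.

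**Conclusion.** The point holds as a missing measurement method that conflicts with the plan's own ICER definition. Applied as written, E.3.a leaves navigator and social worker labour out of the numerator. Provided the QALY difference favours the enhanced arm, this understates the ICER and so favours Hypothesis 3.

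The size cannot be determined from the documents. Under the assumptions shown it runs from trivial ($27 per patient) to large enough to matter against the stated thresholds ($324 per patient with a gain of 0.005 or 0.01), before social worker time.

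This should be fixed, but it does not threaten the trial's main result: the adherence outcome is unaffected, and E.3.d says that the study is not powered on cost-effectiveness.

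**What to change.** In E.3.a:

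1. Define the intervention cost used in the ICER as the resources that differ by arm after randomisation.
2. Add a per-patient log of navigator and social worker contacts with minutes, costed at a job-classification wage plus 35% for each role. This is a new record, since no existing log covers these contacts.
3. Attach unit costs to the interpreter and medication-assistance use already counted in Table 8, and price a given drug equally in both arms even when it is supplied free.
4. Apply the stated travel fares to every recorded follow-up visit in both arms, and say how transport type is obtained for visits at local practices.
5. Keep the exam-step costs for the secondary measure, cost per diagnosis.

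The cost is a change of SAP wording, brief logging by existing staff, and a wage rate for each added role. The ICER will probably look less favourable to the enhanced arm.
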